### **9.9.3 Misclassification**

To minimize misclassification of the recorded patient characteristics, previously validated algorithms or code-lists will be used whenever available. Code-lists were reviewed by qualified medical reviewers prior to implementation. A preliminary study to optimize and validate the algorithm for identification of cases of acute pancreatitis using ICD-9-CM and ICD-10-CM codes was conducted in the [REDACTED]

Some of the major risk factors for acute pancreatitis (e.g. alcohol use, obesity, biliary pathology not requiring reimbursement) are under-reported in claims databases. A similar limitation exists for use of medications known to cause acute or chronic pancreatitis, and it is impractical to account for all of these, even if the data are available. Conversely, the incidence of acute pancreatitis can be overestimated because providers may have used the acute pancreatitis code, abdominal ultrasound or serum lipase measurement to rule out the diagnosis of acute pancreatitis. To mitigate this risk, diagnosis for acute pancreatitis will be assessed using an algorithm that has been validated in the [REDACTED] and shown to have a sensitivity of 89.8% and a specificity of 79.4% [R20-3554]. However, this algorithm does not allow for etiological or pathophysiological description of the type of acute pancreatitis.

Further, the study utilizes a modified as-treated approach as the primary analysis, which could result in exclusion of some cases of acute pancreatitis due to censoring criteria (i.e., patients would be classified as not experiencing acute pancreatitis, but the event could have occurred after censoring). In order to address this, we will perform a sensitivity analysis using an ITT approach. This approach is more conservative and maintains drug classification similar to randomization; however, there is greater risk of exposure misclassification. Ultimately, however, this method will allow for evaluation of potentially additional cases of acute pancreatitis that transpire during the study period given the more limited censoring criteria.

Pancreatitis reoccurs in up to 25% of patients following hospital admission for their first episode of acute pancreatitis, with smoking and/or alcohol abuse demonstrated as predominant risk factors. Smoking and alcohol use could not be measured properly in the US claims databases. Moreover, the baseline period is only 6 months which might result in misclassification of some of recurrent acute pancreatitis events as the first event.

Another important topic to take into account is death which is considered a censoring event, but this information is not well captured in claims databases.

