## **9.5 STUDY SIZE**

All patients with T2DM who newly initiate therapy with empagliflozin or study comparator who meet the inclusion and exclusion criteria will be included in the analysis.

Event rate of acute pancreatitis reported in patients with T2DM who are treated with canagliflozin was reported to be 2.2 per 1000 PY [\[RRA-21430\]](#). This rate was used for sample size calculation using the formula of Farrington and Manning (maximum likelihood method) [\[R14-3295\]](#).

Null hypothesis H0:  $\pi_2 / \pi_1 \geq 1.5$  (non-inferiority)

A single stage (fixed sample size) design was chosen.

For specified  $\alpha = 0.05$  and rates  $\pi_1 = 0.0022$  and  $\pi_2 = 0.0022$  (odds ratio of 1.000) the power (1 -  $\beta$ ) is 80.0% if the test stages consist of the sample sizes given in the last two columns of [Table 1](#).

The computation assumes an allocation ratio (n2/n1) = 1 (Table 1). It is assumed that all patients have 1 year of follow up.

**Table 1** Number of empagliflozin initiators and empagliflozin-exposed person-years needed to detect a HR of 1.5 and 2.0 with a power of 80% and  $\alpha = 0.05$  under 1:1 matching ratio

Hazard ratio (HR)	Information rate	Bunds accept $H_0$	Bunds reject $H_0$	sign.level one-sided	$\alpha$ spent	$\beta$ spent	power achieved	Observations per exposure group	Overall observations
1.5	1.0	1.645	1.645	0.0500	0.0500	-	0.8000	34585.4	69170.8

ADDPLAN Adaptive Design Software 2019 and SAS 9.4 software ( ) were used to calculate the sample size.

Analysis of this study will be initiated as soon as a sufficient sample size to exclude a HR of 1.5 with 80% power is reached. Based on a feasibility assessment conducted in Optum and MarketScan databases using data between 1 August 2014 and the latest data-cut available in MarketScan (30 September 2020) and Optum (31 March 2021), the dual-therapy cohort was reported with the highest number of empagliflozin initiators, therefore meta-analysis of the dual therapy cohorts including the data from the MarketScan and Optum databases will be the main analysis of this study as it will be the only powered analysis.

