### **9.7.6 Sensitivity analysis**

At least the following sensitivity analyses will be performed:

1. All analyses will be performed using an alternate outcome definition using the primary hospitalization discharge diagnosis only (ICD-9-CM 577.0 or ICD-10-CM K85 acute pancreatitis).
2. Exclude cases with ICD-10 K85.2x (Biliary acute pancreatitis) and K85.3x (Alcohol induced acute pancreatitis) and also report the percentage of these cases in overall identified acute pancreatitis cases.
3. Implement an intention-to-treat approach, where all users maintain assignment to their original treatment arm throughout a fixed follow-up period 12 months after first exposure. Users of empagliflozin or a comparator oral non-incretin/non-SGLT2i-containing glucose lowering drugs will be considered exposed from the date of first prescription claim (following a 6-month period without a prescription claim for their index medication) until earliest claim for acute pancreatitis or until one of the following censoring criteria have been met: death, end of registration, or study end. In this analysis, patients discontinuing therapy will not be censored.
4. Subgroup analyses will be performed focusing on patients with and without history of eCVD in the 12 months prior to the index date
5. It is known that Diabetic ketoacidosis (DKA) can be complicated with pancreatitis. As a sensitivity analyses, cases with prior DKA will be excluded.
6. In dual or triple therapy cohorts when the non-index medication (metformin) is discontinued or switched patients will be censored.
7. Considering grace period of 90 days for all medications.

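### The ITT sensitivity analysis is labelled more conservative, but for excluding a hazard ratio of 1.5 its expected bias runs the other way

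*Protocol*

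**What the plan says.** Protocol 9.5 (and the study-size part of the abstract) states the null as a ratio of at least 1.5, labels it "non-inferiority", and tests it one-sided at 0.05. Analysis is to start once a "sufficient sample size to exclude a HR of 1.5 with 80% power is reached".

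The main analysis (9.7.1, 9.7.3) is modified as-treated. Follow-up is censored at discontinuation plus a 30-day grace period, and when an incretin, insulin, another SGLT2 inhibitor or the comparator index drug is added or switched to.

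Sensitivity analysis 3 in 9.7.6 is ITT over a fixed 12 months from first exposure. Only death, end of registration and study end censor. It adds: "In this analysis, patients discontinuing therapy will not be censored".

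Section 9.9.3 offers ITT as the answer to cases lost through as-treated censoring and says: "This approach is more conservative and maintains drug classification similar to randomization". The same sentence concedes more exposure misclassification but does not say which conclusion that favours. SEAP 10.6 only refers back to the protocol.

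**The concern.** Whether an analysis is conservative depends on the null. When the aim is to show a difference, bias towards HR 1 is conservative. When the aim is to reject a ratio of 1.5 or more, the same bias makes rejection easier.

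In the ITT run, time after stopping the index drug, and after adding or moving to the other study drug, still counts to the first drug. If that time carries no drug effect, the arms look more alike than they do on treatment. An ITT upper limit below 1.5 could then be presented as support from the stricter analysis, when under these conditions it is the more lenient one. The plan has no rule for reading a disagreement between the two analyses, so the label is the only guidance a reader of the report would have.

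**Working it through.** **1. The plan's own figure.** Inputs from Protocol 9.5: event rate 0.0022 in both groups, null ratio R = 1.5, one-sided alpha 0.05, power 80%, 1:1 allocation, one year of follow-up each, Farrington-Manning with maximum-likelihood null variance.

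- Restricted null rates: 0.0026398 and 0.0017598 (ratio 1.5).
- Null variance: 0.0026398 × (1 − 0.0026398) + 1.5² × 0.0017598 × (1 − 0.0017598) = 0.0065855.
- Alternative variance: 0.0022 × 0.9978 × (1 + 1.5²) = 0.0071343.
- n = [(1.6449 × √0.0065855 + 0.8416 × √0.0071343) / (0.0022 − 1.5 × 0.0022)]² = 34,585.4 per group, as stated.

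At one-sided 0.025 the figure would be 43,772, so the design does rest on one-sided 0.05. The expected count under HR 1 is 2 × 34,585.4 × 0.0022 = 152 events. The protocol does not say which of its two rates is empagliflozin; the second is assumed here.

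**2. Dilution.** Let f be the share of ITT person-time in the empagliflozin arm spent off the drug. The documents give no value, so f is an assumption and is ranged. With a true on-drug HR of 1.5, a rate ratio of 1 off drug, and an undisturbed comparator arm:

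ITT HR = (1 − f) × 1.5 + f × 1.

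**3. Chance of wrongly excluding 1.5.** Holding person-time at 34,585.4 per group:

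- comparator events e₁ = 34,585.4 × 0.0022 = 76.1
- empagliflozin events e₂ = 76.1 × ITT HR
- SE = √(1/e₁ + 1/e₂)
- P = Φ[(ln 1.5 − ln ITT HR) / SE − z], with z = 1.645, or 1.960 for the upper limit of a 95% CI (the interval planned in 9.7.3).

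For f = 20%: e₂ = 106.5, SE = 0.150, (ln 1.5 − ln 1.40) / SE = 0.0690 / 0.150 = 0.460, and P = Φ(0.460 − 1.645) = 11.8%.

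| f (assumed) | ITT HR | P, one-sided 0.05 | P, 95% CI |
|---|---|---|---|
| 0% | 1.50 | 5.0% | 2.5% |
| 10% | 1.45 | 7.8% | 4.2% |
| 20% | 1.40 | 11.8% | 6.7% |
| 30% | 1.35 | 17.1% | 10.3% |
| 50% | 1.25 | 32.3% | 21.9% |

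The calculation holds person-time, not events, because 152 is the count under HR 1 and more events are expected when the HR exceeds 1. Fixing 152 events would give 11.0% instead of 11.8% at f = 20%.

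**4. How the direction depends on the assumptions, at f = 20%.**

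- If 10% of comparator time is also spent on empagliflozin and carries its risk, the HR falls further: 1.40 / (0.9 + 0.1 × 1.5) = 1.33.
- If off-drug time in the empagliflozin arm has a rate ratio of 1.5 (for example through later treatment), there is no dilution: 0.8 × 1.5 + 0.2 × 1.5 = 1.50.
- If that ratio is 2, the HR rises: 0.8 × 1.5 + 0.2 × 2 = 1.60.

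**The case against.** The strongest reply has four parts.

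- **ITT decides nothing.** As-treated is the primary analysis, the dual-therapy meta-analysis is the only powered one, and ITT is one of seven sensitivity analyses. This stands. A reader might infer that the plan lets a favourable ITT result rescue a failed primary result, or that the primary error rate is inflated. Nothing in the documents says either.
- **The direction is not certain.** This also stands. A reader might infer that ITT must dilute the HR. But ITT retains time after incretins or insulin are added, and the protocol itself cites associations between incretins and acute pancreatitis. If later treatment differs by arm, the HR can move either way, as step 4 shows.
- **The word is loose and partly caveated.** Section 9.9.3 admits misclassification and gives ITT a legitimate purpose, to recover events lost to as-treated censoring. It does not mention the 1.5 margin, and the ENCePP checklist (Annex 2, item 2.1.4) marks the hypothesis question as not applicable. This softens the point but does not remove it: section 9.5 still states the null, and the caveat omits the direction that matters for it.
- **The sizes rest on an assumed f.** True. They illustrate and do not predict, and the 12-month cap limits how large f can be.

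**Conclusion.** The label in 9.9.3 is wrong for the hypothesis in 9.5. If the effect ends on stopping and later treatment is similar in both arms, ITT is expected to move the HR towards 1 and so towards excluding 1.5. With a true on-drug HR at the margin, an off-drug share of 10% to 50% raises the chance of wrongly excluding 1.5 from 5% to between 7.8% and 32.3% (from 2.5% to between 4.2% and 21.9% with a 95% CI). Without those assumptions the direction is open, which does not justify calling the analysis more conservative either.

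The consequence is limited to interpretation. The as-treated test keeps its own error rate, and ITT remains useful as a check on informative censoring.

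**What to change.** - **Section 9.9.3:** delete the claim that ITT is more conservative. State that it addresses informative censoring but, if the drug effect ends on stopping and later treatment is similar by arm, is expected to bias towards HR 1 and hence towards excluding 1.5.
- **Section 9.7.6, item 3:** state that an ITT upper limit below 1.5 cannot on its own support exclusion of 1.5 when the primary as-treated analysis does not exclude it.
- **Reporting:** tabulate, by arm, the share of ITT person-time off the index drug and the share on the comparator drug.

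The first two are wording changes. The table takes modest programming: SEAP 7.1.3 looks for censoring events only within the first continuous exposure to the index drug, so later dispensing episodes and restarts must be reconstructed. The claims needed are already held; no new data, cohort or model is required.

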### **9.9.4 COVID-19 considerations**

Although, there are a lot of unknown details around COVID-19 complications, a few small studies (mainly case reports) reported a possible link between COVID-19 infection and developing acute pancreatitis [R20-1531, R20-1532, R20-1536, R20-3357]. However, two recent observational studies conducted in the Netherlands and Italy suggested that the incidence of acute pancreatitis, as complication of COVID-19 infection, is very low and no

clear etiology was reported [[R21-1729](#), [R21-1730](#)]. Therefore, as an optional analysis, characteristics of patients with acute pancreatitis which were observed after Q1 2020 in these 2 databases will be evaluated to see if we can find any COVID-19 codes in the month prior to acute pancreatitis.

## **9.9.5 Generalizability**

Using a PS-matched analysis within a new user active comparator design decreases channelling bias, but also decreases the representativeness of the final patient cohort. The findings might not be generalizable to all patients with T2DM, especially those on treatment regimens that will not be included in this analysis.

The use of large claims data sources, such as MarketScan and Optum CDM, helps to ensure good representativeness of the US population. Although people over 65 years are under-represented in the MarketScan databases, the use of the Optum CDM data will increase the proportion of people older than 65 years in the analysis.

## **9.10 OTHER ASPECTS**

### **9.10.1 Data quality assurance**

A quality assurance audit/inspection of this study may be conducted by the sponsor or sponsor's designees or by Institutional Review Board (IRBs) / Independent Ethics Committee (IECs) or by regulatory authorities. The quality assurance auditor will have access to all medical records, the investigator's study-related files and correspondence, and the informed consent documentation of this study.

### **9.10.2 Study records**

#### **9.10.2.1 Source documents**

Not applicable.

#### **9.10.2.2 Direct access to source data and documents**

Not applicable.

### **9.10.3 Protocol deviations**

None.

### **9.10.4 Compensation available to the patient in the event of study related injury**

Not applicable.

## **10. PROTECTION OF HUMAN SUBJECTS**

The study will be carried out in compliance with the protocol, the principles laid down in the Declaration of Helsinki, Guidelines for Good Pharmacoepidemiology Practice (GPP), and the relevant BI Standard Operating Procedures (SOPs). Standard medical care (prophylactic,

diagnostic and therapeutic procedures) remains the responsibility of the treating physician of the patient.

## **10.1 STUDY APPROVAL, PATIENT INFORMATION, AND INFORMED CONSENT**

This study will be registered with European Network of Centers for Pharmacoepidemiology and Pharmacovigilance (ENCePP) and on clinicaltrials.gov.

Data are de-identified and comply with the Health Insurance Portability and Accountability (HIPA) Act [[R19-2252](#)], and because this study will not involve the collection, use, or transmittal of individually identifiable data, Institutional Review Board review or approval is not required.

## **10.2 STATEMENT OF CONFIDENTIALITY**

Not applicable.

## **11. MANAGEMENT AND REPORTING OF ADVERSE EVENTS/ADVERSE REACTIONS**

Not applicable based on secondary use of data without any potential that any employee of BI or agent working on behalf of BI will access individually identifiable patient data.

## **12. PLANS FOR DISSEMINATING AND COMMUNICATING STUDY RESULTS**

The principal and co-investigators will lead the development of scientific manuscript(s) of the results to be published. A summary of the main results of the study, whether positive or negative, will always be made available to the public. As per Section V of *Guidelines for Good Pharmacoepidemiology Practices* [[R11-4318](#)] and the *Guideline on Good Pharmacovigilance Practices*, Module VIII, Section B.7 [[R13-5420](#)], the outcome of a study will always be presented in an objective and truthful manner providing a comprehensive and accurate description of the findings. In no way shall the interpretation and presentation of the results be aimed towards any commercial, financial or personal interests.

The principal and co-investigators will write the study report and the results will be reported within the earliest Periodic Benefit Risk Evaluation Report (PBRER). The study results will be published in the EU PAS registry.

## **14. APPENDICES**

### **ANNEX 1. LIST OF STAND-ALONE DOCUMENTS**

None.

## **ANNEX 2. ENCePP CHECKLIST FOR STUDY PROTOCOLS**

Doc.Ref. EMA/540136/2009

### **ENCePP Checklist for Study Protocols (Revision 4)**

Adopted by the ENCePP Steering Group on 15/10/2018

The European Network of Centres for Pharmacoepidemiology and Pharmacovigilance (ENCePP) welcomes innovative designs and new methods of research. This Checklist has been developed by ENCePP to stimulate consideration of important principles when designing and writing a pharmacoepidemiological or pharmacovigilance study protocol. The Checklist is intended to promote the quality of such studies, not their uniformity. The user is also referred to the ENCePP Guide on Methodological Standards in Pharmacoepidemiology, which reviews and gives direct electronic access to guidance for research in pharmacoepidemiology and pharmacovigilance.

For each question of the Checklist, the investigator should indicate whether or not it has been addressed in the study protocol. If the answer is "Yes", the section number of the protocol where this issue has been discussed should be specified. It is possible that some questions do not apply to a particular study (for example, in the case of an innovative study design). In this case, the answer 'N/A' (Not Applicable) can be checked and the "Comments" field included for each section should be used to explain why. The "Comments" field can also be used to elaborate on a "No" answer.

This Checklist should be included as an Annex by marketing authorisation holders when submitting the protocol of a non-interventional post-authorisation safety study (PASS) to a regulatory authority (see the Guidance on the format and content of the protocol of non-interventional post- authorisation safety studies). The Checklist is a supporting document and does not replace the format of the protocol for PASS presented in the Guidance and Module VIII of the Good pharmacovigilance practices (GVP).

**Study title:**

Post-authorization safety study (PASS) to assess the risk of acute pancreatitis in type 2 diabetes mellitus (T2DM) patients newly initiating empagliflozin compared to other oral non-incretin/non-sodium glucose co-transporter-2 inhibitors (SGLT2)- containing glucose lowering drugs

**EU PAS Register® number: EUPAS44267**

**Study reference number (if applicable):**

Section 1: Milestones	Yes	No	N/A	Section Number
1.1 Does the protocol specify timelines for				
1.1.1 Start of data collection 				6

 Date from which information on the first study is first recorded in the study dataset or, in the case of secondary use of data, the date from which data extraction starts.

Section 1: Milestones	Yes	No	N/A	Section Number
1.1.2 End of data collection 				6
1.1.3 Progress report(s)				6
1.1.4 Interim report(s)				NA
1.1.5 Registration in the EU PAS Register®				6
1.1.6 Final report of study results.				6

Comments:

Section 2: Research question	Yes	No	N/A	Section Number
2.1 Does the formulation of the research question and objectives clearly explain:				
2.1.1 Why the study is conducted? (e.g. to address an important public health concern, a risk identified in the risk management plan, an emerging safety issue)				7
2.1.2 The objective(s) of the study?				8
2.1.3 The target population? (i.e. population or subgroup to whom the study results are intended to be generalised)				9.2.2
2.1.4 Which hypothesis(-es) is (are) to be tested?				NA
2.1.5 If applicable, that there is no a priori hypothesis?				NA

Comments:

Section 3: Study design	Yes	No	N/A	Section Number
3.1 Is the study design described? (e.g. cohort, case-control, cross-sectional, other design)				9.1
3.2 Does the protocol specify whether the study is based on primary, secondary or combined data collection?				9.4
3.3 Does the protocol specify measures of occurrence? (e.g., rate, risk, prevalence)				9.7.3
3.4 Does the protocol specify measure(s) of association? (e.g. risk, odds ratio, excess risk, rate ratio, hazard ratio, risk/rate difference, number needed to harm (NNH))				9.7.3

 Date from which the analytical dataset is completely available.

Section 3: Study design	Yes	No	N/A	Section Number
3.5 Does the protocol describe the approach for the collection and reporting of adverse events/adverse reactions? (e.g. adverse events that will not be collected in case of primary data collection)				11

Comments:

Section 4: Source and study populations	Yes	No	N/A	Section Number
4.1 Is the source population described?				9.2.2
4.2 Is the planned study population defined in terms of:				
4.2.1 Study time period				9.2.2
4.2.2 Age and sex				9.2.2
4.2.3 Country of origin				9.2.2
4.2.4 Disease/indication				9.2.2
4.2.5 Duration of follow-up				9.2.2
4.3 Does the protocol define how the study population will be sampled from the source population? (e.g. event or inclusion/exclusion criteria)				9.2.2

Comments:

Section 5: Exposure definition and measurement	Yes	No	N/A	Section Number
5.1 Does the protocol describe how the study exposure is defined and measured? (e.g. operational details for defining and categorising exposure, measurement of dose and duration of drug exposure)				9.3.1
5.2 Does the protocol address the validity of the exposure measurement? (e.g. precision, accuracy, use of validation sub-study)				NA
5.3 Is exposure categorised according to time windows?				9.3.1
5.4 Is intensity of exposure addressed? (e.g. dose, duration)				9.3.1
5.5 Is exposure categorised based on biological mechanism of action and taking into account the pharmacokinetics and pharmacodynamics of the drug?				NA

Section 5: Exposure definition and measurement	Yes	No	N/A	Section Number
5.6 Is (are) (an) appropriate comparator(s) identified?				9.3.1

Comments:

Section 6: Outcome definition and measurement	Yes	No	N/A	Section Number
6.1 Does the protocol specify the primary and secondary (if applicable) outcome(s) to be investigated?				9.3.2
6.2 Does the protocol describe how the outcomes are defined and measured?				9.3.2
6.3 Does the protocol address the validity of outcome measurement? (e.g. precision, accuracy, sensitivity, specificity, positive predictive value, use of validation sub-study)				9.3.2
6.4 Does the protocol describe specific outcomes relevant for Health Technology Assessment? (e.g. HRQoL, QALYs, DALYs, health care services utilisation, burden of disease or treatment, compliance, disease management)				NA

Comments:

Section 7: Bias	Yes	No	N/A	Section Number
7.1 Does the protocol address ways to measure confounding? (e.g. confounding by indication)				9.7
7.2 Does the protocol address selection bias? (e.g. healthy user/adherer bias)				9.9
7.3 Does the protocol address information bias? (e.g. misclassification of exposure and outcomes, time-related bias)				9.9

Comments:

Section 8: Effect measure modification	Yes	No	N/A	Section Number
8.1 Does the protocol address effect modifiers? (e.g. collection of data on known effect modifiers, sub-group analyses, anticipated direction of effect)				NA

Comments:

Section 9: Data sources	Yes	No	N/A	Section Number
9.1 Does the protocol describe the data source(s) used in the study for the ascertainment of:				
9.1.1 Exposure? (e.g. pharmacy dispensing, general practice prescribing, claims data, self-report, face-to-face interview)				9.3.1
9.1.2 Outcomes? (e.g. clinical records, laboratory markers or values, claims data, self-report, patient interview including scales and questionnaires, vital statistics)				9.3.2
9.1.3 Covariates and other characteristics?				9.3.3
9.2 Does the protocol describe the information available from the data source(s) on:				
9.2.1 Exposure? (e.g. date of dispensing, drug quantity, dose, number of days of supply prescription, daily dosage, prescriber)				9.3/9.4
9.2.2 Outcomes? (e.g. date of occurrence, multiple event, severity measures related to event)				9.3/9.4
9.2.3 Covariates and other characteristics? (e.g. age, sex, clinical and drug use history, co-morbidity, co-medications, lifestyle)				9.3/9.4
9.3 Is a coding system described for:				
9.3.1 Exposure? (e.g. WHO Drug Dictionary, Anatomical Therapeutic Chemical (ATC) Classification System)				SEAP
9.3.2 Outcomes? (e.g. International Classification of Diseases (ICD), Medical Dictionary for Regulatory Activities (MedDRA))				9.3
9.3.3 Covariates and other characteristics?				SEAP
9.4 Is a linkage method between data sources described? (e.g. based on a unique identifier or other)				NA

Comments:

--

Section 10: Analysis plan	Yes	No	N/A	Section Number
10.1 Are the statistical methods and the reason for their choice described?				9.7
10.2 Is study size and/or statistical precision estimated?				9.5
10.3 Are descriptive analyses included?				9.7
10.4 Are stratified analyses included?				9.7
10.5 Does the plan describe methods for analytic control of confounding?				9.7

Section 10: Analysis plan	Yes	No	N/ A	Section Number
10.6 Does the plan describe methods for analytic control of outcome misclassification?				9.7
10.7 Does the plan describe methods for handling missing data?				9.7
10.8 Are relevant sensitivity analyses described?				9.7

Comments:

--

Section 11: Data management and quality control	Yes	No	N/ A	Section Number
11.1 Does the protocol provide information on data storage? (e.g. software and IT environment, database maintenance and anti-fraud protection, archiving)				
11.2 Are methods of quality assurance described?				
11.3 Is there a system in place for independent review of study results?				

Comments:

--

Section 12: Limitations	Yes	No	N/ A	Section Number
12.1 Does the protocol discuss the impact on the study results of:  12.1.1 Selection bias? 12.1.2 Information bias? 12.1.3 Residual/unmeasured confounding? (e.g. anticipated direction and magnitude of such biases, validation sub-study, use of validation and external data, analytical methods)	  	  	  	9.7 9.7 9.7
12.2 Does the protocol discuss study feasibility? (e.g. study size, anticipated exposure uptake, duration of follow-up in a cohort study, patient recruitment, precision of the estimates)				9.5

Comments:

--

Section 13: Ethical/data protection issues	Yes	No	N/ A	Section Number
13.1 Have requirements of Ethics Committee/ Institutional Review Board been described?				

Section 13: Ethical/data protection issues	Yes	No	N/A	Section Number
13.2 Has any outcome of an ethical review procedure been addressed?				
13.3 Have data protection requirements been described?				

Comments:

Section 14: Amendments and deviations	Yes	No	N/ A	Section Number
14.1 Does the protocol include a section to document amendments and deviations?				

Comments:

Section 15: Plans for communication of study results	Yes	No	N/ A	Section Number
15.1 Are plans described for communicating study results (e.g. to regulatory authorities)?				12
15.2 Are plans described for disseminating study results externally, including publication?				12

Comments:

Name of the main author of the protocol:

Date: 29/11/2021

Signature: 

